## 4.2 Scientific rationale for the trial design

### 4.2.1 Justification for design and parameters

This trial will examine the effects of food on AEF0117 bioavailability in healthy volunteers. Standard PK parameters will be calculated, and a high fat meal will be served according to current guidance [10].

A parallel-group design has been chosen since detectable plasma concentration has been observed 2 weeks after discontinuation of multiple dosing of 1 mg/day due to the long elimination half-life of AEF0117 in humans. A crossover design would have required a long washout period with a potential risk of a high dropout rate.

As AEF0117 is a lipophilic compound it is anticipated that intake of a high fat meal will introduce a slight food effect i.e., increase the bioavailability, and the trial has been powered for such an effect. A total of 32 participants will be randomized 1:1 to fed or fasted conditions with an aim to complete 14 in each group. In alignment with FDA guidance [10, 11], at least 12 participants will complete the 72-hour PK sample in each group.

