#### **5.4.6 Replacement of participants**

Participants who discontinue prematurely due to safety reasons will not be replaced.

Replacements will take place if more than 4 participants administered trial drug under the same conditions (fasting or fed) drop out for other reasons than safety concern prior to Day 4 (i.e., the 72-hour PK sample).

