**Table 2 Plasma PK parameters**

PK parameter	Definition
$C_{\max}$	maximum observed plasma concentration
$C_{\min,24h}$	minimum observed (or trough) plasma concentration within 24 hours after dosing
$C_{\text{last}}$	last measurable plasma concentration
$T_{\max}$	time to maximum plasma concentration
$T_{1/2}$	terminal elimination half-life
$T_{\text{lag}}$	the delay in achieving $T_{\max}$
$T_{\text{last}}$	time to last measurable plasma concentration
$AUC_{0-24}$	area under the plasma concentration-time curve from time zero (pre-dose) to 24 hours
$AUC_{0-t}$	area under the plasma concentration versus time curve from time 0 (pre-dose) to the last quantifiable concentration time point, calculated using the linear trapezoid rule
$AUC_{0-\infty}$	area under the plasma concentration versus time curve from time 0 (pre-dose) to infinity, calculated using the linear trapezoid rule
CL/F	apparent oral clearance, calculated as dose/ $AUC_{0-\infty}$
% $AUC_{\text{extrap}}$	percentage of $AUC_{0-\infty}$ due to extrapolation from $T_{\text{last}}$ to infinity $([AUC_{0-\infty} - AUC_{0-t}] / [AUC_{0-\infty}]) \times 100$
Vd/F	apparent volume of distribution

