## **9 STATISTICAL METHODS**

### **9.1 Determination of sample size**

The sample size has been chosen based on previous experience in phase 1 studies with AEF0117 where the CV was in the order of 0.3 for  $C_{max}$  and AUC after single doses. It is anticipated that food slightly increases the absorption of AEF0117 and a true ratio of 1.25 is assumed. To allow

for potential participants who dropout early, i.e., not allowing for estimation of  $C_{max}$  and/or  $AUC_{0-t}$ , 32 participants should be included. The power for showing that the upper bound of the 2-sided 90% CI is  $\leq 1.75$  is 90% with 14 participants per treatment group and 86% with 12 participants per group.

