### **9.6.1 Primary endpoint**

The primary analysis will be based on a comparison of the ratio between fed and fasting condition for the following parameters: the mean  $C_{\max}$ ,  $AUC_{0-t}$ , and  $AUC_{0-\infty}$  of each group. Descriptive statistics will be applied to  $T_{\max}$  and  $T_{\text{lag}}$ .

PK analysis will consist of a non-compartmental evaluation of AEF0117 plasma concentration-time profiles to determinate PK parameters using a validated program. PK parameters will be tabulated and summarized using descriptive statistics (mean, median, SD, geometric mean, CV%, minimum, and maximum).

The relative bioavailability will be estimated by calculating the ratio of the geometric means between fed and fasted conditions, based on log-transformed data, for  $AUC_{0-t}$ ,  $AUC_{0-\infty}$  (when appropriate) and  $C_{\max}$ . The 90% CI will be provided. The clinical relevance of any differences between fed and fasted conditions will be discussed, especially with respect to an assessment of the CI in relation to the limits.

An analysis of variance model will be applied, with sequence, period, and state (fed, fasting) as factors.

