## 9.6.2 Secondary endpoints

Additional PK parameters of AEF0117, including  $C_{min,24h}$ ,  $t_{1/2}$ , %AUCextrap, CL/F, and Vd/F will be calculated using non-compartmental methods and summarized by graphic displays and descriptive statistics as data permit. Individual and summary (means  $\pm$  SD for each condition i.e., fed/fasting) plasma AEF0117 concentration-time plots will be displayed graphically.

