## 9.8 Participant withdrawals and missing data

All data will be included and used as recorded. Specific participants and/or data may be excluded from the PK analysis as described in [9.2.3](#).

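### Do participants who leave after the 72-hour sample spoil the AUC0-t comparison, so that a supportive AUC0-72h ratio is needed?

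*Protocol*

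**What the plan says.** Protocol Table 2 (section 7.2.3) defines AUC0-t as the area from time 0 "to the last quantifiable concentration time point, calculated using the linear trapezoid rule". Section 9.6.1 makes it a primary compared parameter, beside Cmax and, when appropriate, AUC0-inf: "The relative bioavailability will be estimated by calculating the ratio of the geometric means between fed and fasted conditions, based on log-transformed data". Samples are drawn up to 312 hours.

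Two rules refer to 72 hours. Section 4.2.1 requires that "at least 12 participants will complete the 72-hour PK sample in each group". Section 5.4.6 triggers replacement only when more than four participants in one condition drop out before Day 4 for non-safety reasons.

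Other provisions also bear on the point:

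- Section 4.2.1 aims to complete 14 per group out of 32 randomized, and section 9.2.1 defines completion as completing the Day 14 follow-up visit.
- Section 9.1 allows "for potential participants who dropout early, i.e., not allowing for estimation of" Cmax and/or AUC0-t.
- Section 9.2.3 limits the PK population to participants with sufficient and valid concentrations. A documented review before database lock can exclude a participant or specific data.
- Section 9.8 states "All data will be included and used as recorded", subject to those exclusions.
- Sections 5.4.1 and 8.1.6 ask for the follow-up assessments, including a PK sample, at early termination.
- Section 9.3 promises a SAP before the first dose.

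**The concern.** The explicit head-count rules stop at 72 hours, yet AUC0-t ends at each participant's own last quantifiable time. Section 4.2.1 reports that "detectable plasma concentration has been observed 2 weeks after discontinuation of multiple dosing of 1 mg/day due to the long elimination half-life", so a participant could well leave while still quantifiable. Five of the seven post-discharge visits (Days 5, 7, 9, 11 and 14) come after the 72-hour sample. A shortened area differs from a full one for a reason unrelated to food. In a parallel-group trial that difference goes straight into the between-participant variance, and it shifts the observed ratio if leavers fall unequally between arms. No area over a common observed window is compared, since AUC0-24 is defined but does not appear in section 9.6.1. If the effect were real and sizeable, the stated 90% power would be overstated for AUC0-t, and an AUC0-72h ratio would be a cheap safeguard.

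**Working it through.** **1. The plan's own figure.** Inputs from section 9.1: CV 0.3, true ratio 1.25, limit 1.75, two-sided 90% CI.

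- Log-scale SD: σ = √ln(1 + 0.3²) = 0.2936. Distance to the limit: δ = ln(1.75/1.25) = 0.3365.
- With n per group, SE = σ√(2/n), and power comes from the noncentral t with 2n − 2 degrees of freedom and noncentrality δ/SE.
- n = 14: SE = 0.1110, noncentrality 3.03, power 90.4%.
- n = 12: SE = 0.1198, noncentrality 2.81, power 85.9%.

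The stated 90% and 86% are reproduced. The same formula gives 88% at 13 and 93.6% at 16 per group.

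**2. Who counts among the 14.** The concern needs a post-72-hour leaver to be one of the 14. Section 4.2.1 speaks of completing 14 per group, and section 9.2.1 ties completion to Day 14. Read together, the 14 are Day 14 completers, and 16 − 14 = 2 leavers per arm are already allowed for. The 72-hour figure of 12 is a minimum per group. It does not define whose AUC0-t is sufficient; section 9.2.3 governs that.

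**3. Size of the effect.** The half-life, the rate of late leaving and its timing are not stated, so all three are assumed. A leaver at time T keeps a share r of their AUC to 312 hours.

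- Mono-exponential: r(T) = (1 − e^(−kT))/(1 − e^(−312k)), with k = ln 2/half-life. At 72 hours r = 0.88 / 0.65 / 0.53 / 0.37 for half-lives of 24 / 48 / 72 / 150 h.
- Two-phase, half the area in an 8-hour fast phase: r = 0.94 / 0.83 / 0.77 / 0.73.

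Leaving with probability p, regardless of arm, adds about p(1 − p)(ln r)² to the log variance of 0.0862. At p = 2/14 and 150 h:

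- Mono-exponential: 0.1224 × 0.983 = 0.120, so the SD becomes √0.2066 = 0.45.
- Two-phase: 0.1224 × 0.1025 = 0.0125, so the SD becomes √0.0987 = 0.31.

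Simulated power against 1.75, with no early-termination sample:

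| Case (half-life) | 24 h | 48 h | 72 h | 150 h |
|---|---|---|---|---|
| Mono-exponential, all leave at 72 h, 2/14 | 90% | 84% | 76% | 61% |
| Mono-exponential, leaving spread over 72–240 h, 2/14 | 90% | 88–89% | 85% | 77% |
| Two-phase, all leave at 72 h, 2/14 | 90% | 89% | 88% | 87% |
| Mono-exponential, all leave at 72 h, 2/16 | 93% | 89% | 82% | 68% |
| Mono-exponential, leaving spread over 72–240 h, 2/16 | 94% | 92% | 90% | 83% |
| Two-phase, all leave at 72 h, 2/16 | 93–94% | 93% | 92% | 91% |

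The 2/14 rows start after two of 16 have already been lost, so on average four of 16 per arm are not fully sampled. Excluding all four leaves 12 and 86%, which section 9.1 already states. Excluding two of 16 leaves 14 and 90%.

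**4. The companion parameter.** On the mono-exponential curve that produces the large losses, AUC0-inf from a profile cut at 72 hours is 0.99–1.00 of its full value, and section 9.6.1 already compares it. On two-phase curves with 25–50% of the area in the fast phase, AUC0-inf from a cut profile is less dependable (0.98 at 24 h down to 0.60 at 150 h). With half the area in that phase, however, AUC0-t itself loses little power.

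**5. Validity.** When leaving does not depend on arm, the mean ratio is 1.25 and 90% CI coverage is 0.90 in every case simulated.

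**6. What the addition would change.** AUC0-t, AUC0-inf, the power statement and all the rules would stay as they are. AUC0-72h captures 88 / 65 / 53 / 37% of the area to 312 hours on the mono-exponential curve, so it says least about total exposure where the alleged problem is largest.

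**The case for a change.** The strongest reply has three parts.

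First, section 9.1 describes its allowance in terms of participants whose AUC0-t cannot be estimated, and a leaver at 96 hours does yield an AUC0-t. Taken alone, that wording puts such a person among the evaluable. This stands as a looseness. It is outweighed by the completion target in section 4.2.1 and the definition in section 9.2.1, and section 9.1 nowhere says that late leavers make up the 14.

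Second, keeping shortened areas can cost more power than dropping them: 84 / 76 / 61% against 86% at 12 per group, for mono-exponential half-lives of 48 / 72 / 150 h. That arithmetic is right under its assumptions, and exclusion at the pre-lock review is discretionary. The review does exist, however, and it can remove one parameter while keeping Cmax.

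Third, two leavers in only one arm of 14 would move the ratio to 1.25 × r^(2/14) or its inverse. At 72 hours on the mono-exponential curve this gives 1.23 down to 1.08 (fed) or 1.27 up to 1.44 (fasted). That is correct as arithmetic, but nothing in the protocol suggests that late leaving depends on the arm, and chance imbalance is already reflected in the CI, whose coverage holds. %AUCextrap, disposition by time, listings and the individual plots ("plasma AEF0117 concentration-time plots will be displayed graphically") would show any truncation.

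It also remains true that the early-termination sample is lost if consent is withdrawn or contact fails, and that no common-window area ratio is planned in the protocol.

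**Conclusion.** There is no error, contradiction or badly fixed rule here. AUC0-t is correctly defined, its ratio and CI remain valid when leaving is unrelated to arm, and the stated 90% and 86% reproduce. The 16 randomized per arm leave room for two late leavers before the 14 is breached. The large power losses (61–76%) need several unstated assumptions at once: 2 of 14 per arm leaving, all at 72 hours, a mono-exponential curve with a half-life of 72 hours or more, and no early-termination sample. With half the area in an 8-hour fast phase, power is 87–90% at 2/14 and 91–94% at 2/16. If nobody leaves late, or concentrations fall below quantification soon after 72 hours, the effect is about nil. The documents give no half-life or late drop-out rate, so a long mono-exponential profile cannot be ruled out; on that profile the planned AUC0-inf comparison largely covers the gap. An AUC0-72h ratio would be a reasonable supportive output, and the SAP promised in section 9.3 is its natural place. Its absence from the protocol is not a finding.

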## 7.3 Adverse events

### 7.3.1 Definition of adverse events and serious adverse events

#### Adverse event

An AE is defined as any untoward medical occurrence in a clinical trial participant which is temporally associated with the use of a trial intervention, and which does not necessarily have a causal relationship with the intervention. The definition also covers medication errors and uses outside what is foreseen in the protocol, including misuse and abuse of the trial drug.

An AE can therefore be any unfavorable and unintended sign (including an abnormal laboratory finding), symptom, or disease temporally associated with the use of an investigational medicinal product, whether or not considered related to the investigational medicinal product.

An AE may therefore be:

- A new symptom/disease/condition.
- Worsening (increase in frequency or severity) of a pre-existing symptom/disease/condition.

#### Clinically significant laboratory abnormalities

Any laboratory abnormalities which are considered clinically significant by the investigator must be reported as AEs. A clinically significant abnormality is a confirmed abnormality (by 1 repeat test) resulting in the participant being symptomatic, requiring corrective treatment or additional examinations, or if the laboratory value leads to discontinuation of the participant from the trial, and/or fulfills a seriousness criterion. In the evaluation of whether laboratory abnormalities are

clinically significant, local laboratory reference values, relevant baseline parameters, medical history, concomitant medications, and concomitant symptoms reported as AEs should be considered.

Whenever possible, the etiology of the abnormal findings will be documented on the eCRF. Repeated additional tests and/or other evaluations required to establish the significance and etiology of an abnormal result should be obtained when clinically indicated.

### **Other clinically significant safety assessments**

Any changes from baseline in other safety assessments (e.g., vital signs measurements, ECGs, physical examinations), which are considered clinically significant in the judgment of the investigator should be reported as AEs.

### **Surgical procedures**

Surgical procedures (e.g., appendectomy) are not AEs, but the condition for which the surgery is required may be an AE if it occurs or is detected during the trial period. Planned surgical measures permitted by the clinical trial protocol and the condition(s) leading to these measures are not AEs, if the condition(s) was (were) known before the start of the trial treatment. In the latter case, the condition should be reported as medical history.

### **Serious adverse event**

An SAE is any medical occurrence that:

- Results in death.
- Is life-threatening at the time of the event as it occurred, i.e., the participant was at an immediate risk of death at the time of the SAE (not an event, which hypothetically might have caused death, if it was more severe).
- Requires inpatient hospitalization or prolongation of an existing hospitalization (involving at least an overnight stay for observation and/or treatment that would not have been appropriate in the physician's office or in an outpatient setting). Hospitalization for elective treatment of a pre-existing condition that did not worsen from baseline is not considered an AE.
- Results in persistent or significant disability/incapacity defined as a substantial disruption of a person's ability to conduct normal life functions. Events of relatively minor medical significance such as uncomplicated headache, vomiting, diarrhea, and accidental trauma such as a sprained ankle do not constitute a substantial disruption.
- Is a congenital anomaly/birth defect.
- Is an important medical event that, when based upon appropriate medical judgment may jeopardize the participant or may require medical or surgical intervention to prevent one of the outcomes listed above. Examples of such events include allergic bronchospasm requiring intensive treatment at an emergency room or at home, blood dyscrasias, convulsions that do not result in hospitalization, or the development of drug dependency or drug abuse.

### **7.3.2 Time period and frequency for collection of adverse event and serious adverse event**

All AEs will be collected in this trial at each visit starting after the informed consent for trial participation has been signed and until the follow-up visit (Day 14).

Signs and symptoms present prior to dosing of the trial drug that would qualify as an AE if presented later, should be recorded as AEs in the eCRF with date/time of occurrence, to be able to evaluate any increase in severity during treatment, and will be designated pre-treatment-emergent AEs. AEs that are not present at baseline, or if present at baseline, have worsened in severity after dosing of AEF0117 on Day 1 will be considered treatment-emergent AEs (TEAEs).

The investigator is not obligated to actively seek information on AEs or SAEs after a participant has concluded trial participation. However, if the investigator detects an SAE in a trial participant after the end of the period of observation, and considers the event possibly related to prior trial treatment, he/she should promptly contact the sponsor to determine how the event should be documented and reported.

### **7.3.3 Method of detecting adverse events and serious adverse events**

Care will be taken not to introduce bias when detecting AEs and/or SAEs. AEs may be reported spontaneously by the participant, after a general non-leading question by the investigator (e.g., “How are you today”), or be observed by the investigator or designee (e.g., vomiting, or a clinically significant abnormal change from baseline in a laboratory parameter).

### **7.3.4 Assessment and recording of adverse events and serious adverse events**

The investigator is responsible for ensuring that all AEs (as defined in section [7.3.1](#)) are recorded in the participants’ source document and the eCRF.

The following information should be recorded for all AEs: diagnosis, start and stop date and time, severity and seriousness of the event, investigator’s opinion of causality, action taken regarding the trial drug, other action taken, treatment given for the AE, and resolution/outcome.

#### **7.3.4.1 Nature of the adverse event**

The AE should be reported in standard medical terminology. If known, the diagnosis of the underlying illness or disorder should be recorded, rather than its individual symptoms. If a definitive diagnosis is not possible, the individual symptoms and signs should be recorded.

#### **7.3.4.2 Intensity/severity of the adverse event**

The severity of an AE will be graded according to the scale below. The severity of the AE is determined by the principal investigator, who may consult with the sponsor’s medical monitor, if needed.

- *Mild*: A sign or symptom that do not disrupt usual activity.
- *Moderate*: A sign or symptom with sufficient intensity to affect usual activity (disturbing).

- *Severe*: A sign or symptom resulting in considerable interference with the participant's daily activities (unacceptable).

When the intensity of an AE worsens over time for a reporting period (e.g., between visits, etc.), each increase in intensity will be reported as a new AE until the event resolves.

#### 7.3.4.3 Duration of the adverse event

The duration of the AE will be described by the start and stop date and time.

#### 7.3.4.4 Adverse event causality

The investigator must assess the relationship between the trial intervention and each occurrence of each AE using clinical judgment. The relationship or association of the AE to the trial drug will be characterized as related or not related by the investigator using the following classification:

- *Related*: The temporal relationship of the AE with the trial drug makes causality probable or possible and the AE cannot be due to another cause such as other drugs, a surgical intervention, or an underlying disease.
- *Not related*: The temporal relationship of the AE with the trial drug makes causality unlikely or certainly not related and/or the AE can be due to another cause such as other drugs, a surgical intervention, or an underlying disease.

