### **5.4.2 Treatment discontinuation**

In this trial, the 2 randomized groups may be divided into smaller cohorts of minimum 2 participants that are dosed sequentially for operational reasons. Administration of trial drug to participants scheduled to be dosed should be discontinued, at least temporarily, until a thorough evaluation of safety and relationship to trial drug has been performed, for any of the following reasons:

- Trial drug-related SAE in 1 participant in a cohort, or 2 or more trial drug-related SAEs of the same character across cohorts.
- Trial drug-related severe AE in 1 participant and AEs of the same character but less severe in the other participants in a dosing cohort (or severe AEs of the same character in one third of participants across at least 3 cohorts).
- Findings that, at the discretion of the investigator and/or sponsor, indicate that trial drug administration should be discontinued.

In case of unresolved relationship to trial drug for SAEs or severe AE in 1 participant and AEs of the same character but less severe in the other participants in a cohort (or SAEs of the same character across cohorts, or severe AEs of the same character in one third of participants across at least 3 cohorts), the trial may be temporarily interrupted/further dosing postponed. Except in cases of emergency, it is recommended that the investigator consult with the sponsor medical monitor (or other representative of the sponsor) before temporarily interrupting the trial. The investigator must obtain approval from the sponsor medical monitor before restarting dosing of the next cohort.

All patients who have been dosed with AEF0117 will be encouraged to continue to attend trial center visits through the 2-week post treatment follow-up visit to have safety assessments performed as scheduled.

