#### 7.3.5 Reporting of adverse events

All AEs must be recorded in the AE module in the eCRF, regardless of severity or apparent relatedness to dosing of the trial drug.

AEs classified as serious must be reported to the sponsor's designee immediately using the SAE form (see section [7.3.6](#)).

Any clinically significant laboratory abnormalities that are either unexplained or considered treatment related should be discussed with the sponsor's medical monitor.

Additional non-protocol-specified laboratory tests performed if deemed necessary by the investigator or required by local regulations must be recorded on the eCRF.

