### 7.3.7 Suspected adverse reactions

Suspected adverse reaction means any AE for which there is a reasonable possibility that the drug caused the AE. 'Reasonable possibility' means there is evidence to suggest a causal relationship between the drug and the AE. A suspected adverse reaction implies a lesser degree of certainty about causality than adverse reaction, which means any AE caused by a drug.

The PV vendor will notify any Suspected Unexpected Serious Adverse Reaction (SUSAR) to the FDA. This notification will be made within a period of 15 calendar days since the sponsor has knowledge of the SUSAR and 7 days, if the SUSAR has caused death or was life-threatening.

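### Section 7.3.4.4 codes an AE as related only if no other cause could explain it, a stricter bar than the reasonable-possibility standard in 7.3.7, so the related-AE count can only be lowered

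*Protocol*

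**What the plan says.** Section 7.3.4.4 asks for clinical judgment on each AE, but the result must be recorded "as related or not related by the investigator using the following classification". There are two categories.

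- *Related*: the timing "makes causality probable or possible and the AE cannot be due to another cause". Other drugs, surgery and underlying disease are given as examples of such causes.
- *Not related*: the timing makes a drug cause unlikely or rules it out, "and/or the AE can be due to another cause", with the same examples.

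Section 7.3.7 sets a different standard: "Suspected adverse reaction means any AE for which there is a reasonable possibility that the drug caused the AE". It explains this as evidence suggesting a causal relationship and says that it implies less certainty than an adverse reaction proper.

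Relatedness is then used in these places:

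- Section 9.7.2 and the synopsis tabulate related and not-related AEs.
- Section 5.4.2 lists dosing-hold triggers that begin "Trial drug-related SAE in 1 participant in a cohort" and "Trial drug-related severe AE in 1 participant".
- Section 7.3.5 states: "Any clinically significant laboratory abnormalities that are either unexplained or considered treatment related should be discussed" (with the medical monitor).
- Section 5.4.1 extends safety follow-up for toxicities related to the trial drug.

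**The concern.** The *related* category joins two conditions with *and*, and the second requires that no other cause could account for the event. That is a test of exclusion, not of plausibility. Most AEs in a single-dose volunteer study are non-specific, and a competing explanation can often be named. An investigator who follows the text has no category for an event that is possibly drug-related with other causes not excluded, and has to record it as not related.

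Safety and tolerability is a stated secondary objective with AEs as an endpoint (section 3), so the related-AE table is one of its direct outputs. The same word also governs operational decisions: whether dosing is held, whether a laboratory abnormality goes to the medical monitor, and whether follow-up is extended. Because the code is assigned event by event at the site, an analysis plan cannot recover a causality judgment that was collected under the narrower definition.

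**Working it through.** No figure in the protocol needs reproducing. The check is logical, followed by one piece of arithmetic on step size.

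**Definitions.** Let T mean that the timing makes a drug cause probable or possible. Let A mean that the event can be due to another cause.

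- 7.3.4.4 *related* = T and not A.
- 7.3.4.4 *not related* = not T, or A.

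The second is the exact complement of the first. Every assessed event therefore falls in one category only, and the two bullets confirm each other. This is the operative rule, not a slip in one line.

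**Comparison with 7.3.7**

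| Drug link (T) | Other cause can explain (A) | Code under 7.3.4.4 | Can meet 7.3.7? |
|---|---|---|---|
| yes | no | related | yes |
| yes | yes | not related | yes |
| no | no | not related | no |
| no | yes | not related | no |

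Section 7.3.4.4 codes 1 of 4 cells as related, while the 7.3.7 standard can be met in 2 of 4. Only the second row differs, and it moves from related to not related. No row moves the other way, so the added condition leaves the related count unchanged or lowers it. The cells are logical cases and say nothing about how often each occurs.

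**Step size.** Section 4.1 plans 16 participants per group and 32 in total. If all are dosed, one participant whose only possibly related AE lies in the second row changes related-AE incidence by

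- 1/16 = 6.25 percentage points in that group;
- 1/32 = 3.125 percentage points overall.

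**Where the code bites**

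- *5.4.2.* Two of the three listed triggers open with a drug-related event. The first can fire on one participant, so a single code can decide whether that trigger is met. The alternative limb of the second trigger, severe AEs of the same character in one third of participants across at least 3 cohorts, has no relatedness wording of its own. The third trigger is discretionary.
- *7.3.5.* The discussion rule covers laboratory abnormalities that are unexplained or considered treatment related. A second-row abnormality has another explanation and is coded not related, so it can miss both conditions.
- *5.4.1 with 7.3.9.* Section 5.4.1 extends follow-up for drug-related toxicities. Otherwise 7.3.9 leaves unresolved non-serious AEs at the follow-up visit to the investigator's discretion.

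**The case against.** The strongest reply accepts the mismatch and disputes its weight.

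**Different functions.** Section 7.3.7 defines a regulatory term and gives SUSAR notification to the pharmacovigilance vendor, whereas 7.3.4.4 is the investigator's code. SAEs from dosing onward go to the sponsor within 24 hours regardless of relationship (7.3.6). This stands: initial SAE reporting does not depend on the code. It does not explain why the site should judge causality by a stricter test.

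**Few rival causes.** The named examples are largely screened out by exclusion criteria 2 and 15 and the medication limits in 6.7.2. This stands in part, and the number of events affected may be small or zero. But the examples are only illustrative. Section 2.3.1 lists headache, dizziness, dyspepsia, nausea and raised CPK among earlier AEs. Blood drawing (which section 2.3.1 says may cause lightheadedness), the 10-hour fast, the high-fat meal and caffeine abstinence could each be offered as a rival cause for some of these. That link is an inference, as the protocol gives no rates. The meal condition differs by arm, so the available explanations could differ by arm too.

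**Backstops exist.** Section 5.4.2 keeps a discretionary trigger and an optional pause when relationship is unresolved. Clinically significant laboratory abnormalities are monitored to resolution (7.3.9), and the sponsor is notified if they do not normalise (7.4.1.1). These soften the consequence. The pause is only permitted, however, and an event coded not related is arguably no longer unresolved. In addition, 5.4.1 and 5.4.2 do not cite 7.3.4.4. Reading its definition into them is an inference, though it is the protocol's only relatedness classification.

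**Weaker contrasts.** Section 7.3.2 asks for sponsor contact if the investigator "considers the event possibly related to prior trial treatment" for an SAE found after participation ends. That is a contact rule, not a coding standard. Counting missing causality as related in 9.7.2 is an ordinary conservative default. Neither is needed for the conclusion.

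**Conclusion.** The definition is wrong as written. It forces possibly or probably drug-caused events with any rival explanation into the not-related category, it conflicts with the standard in 7.3.7, and its only possible effect on the related count is downward.

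The conclusion assumes that investigators apply 7.3.4.4 literally, as its wording requires. The number of AEs affected cannot be computed from the protocol; the 6.25-point step shows only what one recoded participant does in a group of 16. The certain consequence is for the related/not-related table. The effects on dosing holds, medical-monitor discussion and follow-up hold if those sections use the 7.3.4.4 classification.

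The all-AE tables by group, SAE reporting to the sponsor, follow-up of SAEs and of clinically significant laboratory abnormalities, and the PK analysis are unaffected. This should be corrected, but it does not threaten the primary objective.

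**What to change.** In 7.3.4.4, define *related* as a reasonable possibility that the trial drug caused the AE, even if other causes may have contributed. Define *not related* as no reasonable possibility. Delete the alternative-cause clause from both categories. Rival explanations can still be weighed in reaching the judgment, but they should not disqualify an event on their own. A softer edit that excludes events more likely due to something else would still set a higher bar than 7.3.7. State that this classification applies in 5.4.1, 5.4.2, 7.3.5 and 9.7.2, and align the eCRF guidance before AEs are assessed.

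The cost is a wording change in one section and in the eCRF guidance, a somewhat higher count of related AEs, and possibly an occasional extra dosing pause. Sample size, schedule and PK analysis do not change.
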